4.3.4.7 NUMERIC RATING SCALE (NRS)

The study subjects will be asked to complete a 11-point Numeric Rating Scale (NRS)²⁰ for the level of pain and discomfort associated with the study procedure. The average pain score for the entire region treated will be recorded. Directions to subject will be: "Please rate the average pain you are experiencing in the treatment area on a scale of 0-10, with 0 being 'Best/No Pain' and 10 being the 'Worst Possible Pain'."

Pain will be defined in this study as the average pain reported in the treatment area using the following categories: None (Score of 0), Mild (Score of 1-5), Moderate (Score of 6-7), and Severe (Score of 8-10). Classifications of NRS pain scores have been documented in literature²⁰. Moderate and severe pain/discomfort are considered Adverse Events (AE). Severe subject reported pain does not necessarily correlate to a "severe" adverse event classification. Events will be classified by investigator based on clinical evaluation, the effect to daily activities, and mitigation needed as per **Section 8** of this protocol.

Subjects experiencing pain adverse events will be considered resolved when their pain score is documented as returning to a 0 score.

Numeric Rating Scale will be completed pre-treatment, post-treatment, and at all follow-up visits to capture pain scores.

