4. STUDY DESIGN AND ENDPOINTS

4.1 DESCRIPTION OF THE STUDY DESIGN

This is a prospective, multi-center, non-randomized, single-arm study of up to 16 subjects treated with the Renuvion APR System. Subjects will receive treatment with the Renuvion APR System in the lower periorbital area on both sides of the face.

At baseline, images will be taken utilizing the site's camera system. Baseline images will be used as comparator images for follow-up images for Independent Photographic Reviewer evaluation and subject/investigator assessments.

The treatment area will be tumesced with 20 - 25ml of fluid on each side of the periorbital area.

The treatment of the periorbital area will be accessed from an incision placed in the crease of the lower lid. Two incisions will be placed in both the medial and lateral crease of the lower lid. Treatment will be performed through one incision and the second incision will be used to allow for adequate venting of helium gas. Care will be taken to undermine the tissue and to ensure the incisions communicate with each other to allow adequate venting. An optional third lower lid incision may be made as needed. The treatment plane will be above the orbicularis muscle. The treatment settings will be 60-70% Power, 1 LPM, and 3 Passes. Procedure data and adverse events will be captured.

Follow-up will occur 1 day, 3 days, 7 days, 30 days, 90 days, and 180 days post-procedure; images will be taken at all visits. Investigator/subjects assessments will be completed at D30, D90, and D180 visits. Subjects may also be seen back for follow-up at the investigator's discretion.

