4.3.2 PRIMARY SAFETY ENDPOINT

The primary safety endpoint is an analysis of adverse events through the D180 post-treatment visit.

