7.4 SUBJECT RANDOMIZATION AND TREATMENT GROUP ASSIGNMENT

No randomization. Subjects will receive treatment with the Renuvion APR System in the lower eyelid area on both sides of the face.

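### Section 4.3.4.7 sets the pain adverse-event trigger on one average score over both treated lids, so pain confined to one lid can be classed as Mild and miss the trigger

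*Combined protocol and SAP*

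**What the plan says.** Section 4.1 (Description of the Study Design) makes the treatment bilateral: "Subjects will receive treatment with the Renuvion APR System in the lower periorbital area on both sides of the face". Section 7.4 repeats this.

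Section 4.3.4.7 (Numeric Rating Scale) takes one pain score per subject per time point: "The average pain score for the entire region treated will be recorded". The subject is told: "Please rate the average pain you are experiencing in the treatment area on a scale of 0-10". The score is then categorised: "Pain will be defined in this study as the average pain reported in the treatment area using the following categories". The cut-offs are None 0, Mild 1-5, Moderate 6-7 and Severe 8-10. The section continues: "Moderate and severe pain/discomfort are considered Adverse Events (AE"). On the scale, the trigger is therefore a score of 6 or more.

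Neither Section 4.3.4.7 nor Table 6 provides a score per side or a worst-pain score. The synopsis and Section 4.3.3 list the same regional average as secondary outcome 8.

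Section 4.3.4.7 also says that a Severe pain score need not mean a severe event, and that the investigator classifies events clinically under Section 8. Section 4.3.2 states: "The primary safety endpoint is an analysis of adverse events through the D180 post-treatment visit".

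**The concern.** The two lids are separate treatment sites, and several local risks listed in Section 2.2.1 (burn, hematoma, infection, nerve injury) can affect one side only. An average over both sides can never exceed the score of the worse side, so any distortion from averaging runs in one direction. It is largest when all the pain is on one side.

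Two things are at stake. One is the score-based pain trigger, the only pain-specific adverse-event threshold in the protocol. The other is the summary of pain scores for secondary outcome 8. Consistency is a further issue. Because the meaning of the average is not explained, two subjects with the same one-sided pain could give different answers and fall on different sides of the trigger.

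**Working it through.** The plan gives no figure of its own to reproduce here. The check maps pairs of side scores through the plan's categories.

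**Inputs from the protocol**
- Sides treated: 2 (Sections 4.1 and 7.4).
- Categories: 0 None, 1-5 Mild, 6-7 Moderate, 8-10 Severe (Section 4.3.4.7).
- Pain trigger: score of 6 or more (same section).

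**Assumptions**
- Each side has weight 0.5 in the subject's average; varied from 0.5 to 0.8 below.
- The other side scores 0, which is what pain confined to one lid means; higher values are shown in step 2.

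**Step 1. Pain on one side only, equal weights.** Average = (painful side + 0)/2.

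| Painful side | Average | Category of average | Category of that side alone |
|---|---|---|---|
| 6 | 3.0 | Mild | Moderate |
| 7 | 3.5 | Mild | Moderate |
| 8 | 4.0 | Mild | Severe |
| 9 | 4.5 | Mild | Severe |
| 10 | 5.0 | Mild | Severe |

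The maximum is 5.0, so no one-sided score reaches 6.

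**Step 2. Some pain on the other side.** An average of 6 needs the two scores to sum to 12. The other side must therefore score at least 12 - 8 = 4, 12 - 9 = 3 or 12 - 10 = 2 when the painful side is 8, 9 or 10.

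There are 11 x 11 = 121 ordered whole-number pairs, and 8 x 8 = 64 of them have both sides at 7 or less. That leaves 121 - 64 = 57 with at least one side at 8 or more.
- Average of 5 or less: (8,0), (8,1), (8,2), (9,0), (9,1), (10,0), in either order, so 6 x 2 = 12 pairs.
- Average of 5.5: (8,3), (9,2), (10,1), in either order, so 3 x 2 = 6 pairs. A whole-number rating would be 5 or 6.
- Average below 6 in total: 12 + 6 = 18 of 57.

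These counts describe the rule. They are not probabilities, because the documents do not say how often each pair occurs.

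**Step 3. Unequal weights, other side 0.** Average = weight x painful side.

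| Weight on painful side | 8 | 9 | 10 |
|---|---|---|---|
| 0.5 | 4.0 | 4.5 | 5.0 |
| 0.6 | 4.8 | 5.4 | 6.0 |
| 0.7 | 5.6 | 6.3 | 7.0 |
| 0.8 | 6.4 | 7.2 | 8.0 |

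A one-sided 10 meets the trigger once its weight reaches 6/10 = 0.6. At weight 0.8, one-sided scores of 8, 9 and 10 all meet it.

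**Step 4. Same cut-offs applied to the higher side.** One-sided 6 and 7 become Moderate, and 8, 9 and 10 become Severe. All five meet the trigger, against none under equal weighting.

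**The case against.** The strongest reply is that the protocol never computes a mean of two side scores. The subject gives one rating, no weights are stated, and the average could be read as over time. A subject with one very painful lid might simply answer 8. This stands. A reader might infer that severe one-sided pain is always classed as Mild, but the text supports only that it can be.

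Second, a reader might infer that pain scored 5 or less cannot be an adverse event. Section 4.3.4.7 does not say so, and it leaves classification to the investigator under Section 8. Section 8.1.1 defines adverse events to include any untoward symptom and limits expected treatment effects to mild or moderate severity. Section 8.2.1 grades severity by interference with daily activity, not by the pain score. Section 8.3 requires an interview at each follow-up visit and allows an expected effect to be re-categorised. This also stands, with one limit: pain is a listed expected treatment effect (Section 2.2.1), so a score in the Mild range has a ready label that is not an adverse event.

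Third, the complications that make the concern vivid would be recorded anyway. Burn, hematoma and infection are listed in Section 2.2.1 apart from the expected effects, and the synopsis (Safety Variables) has the treatment area visually examined at each visit. What can be lost is the pain event, not the complication. This stands for visits in person. Virtual visits, including by telephone, are allowed under Follow-up Visits in Section 7, and a telephone call gives no view of the lid.

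Finally, nothing in the documents suggests that strongly one-sided pain is common when both lids receive the same treatment. That is fair, and no frequency is claimed here.

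**Conclusion.** The point holds as a limited weakness of measurement. With a literal reading and equal weights, pain confined to one lid scores at most 5, is classed as Mild and does not trigger a pain adverse event, even at 10 out of 10 on that side. The result depends on those two assumptions. For a one-sided 10 it fails once the painful side carries a weight of 0.6 or more. For a 10 at equal weights it fails once the other side scores 2 or more.

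The effect reaches the score-based trigger and the summaries for secondary outcome 8. A reader might go further and infer that the primary safety endpoint is understated in general. The documents do not show that, because the other routes to an adverse event under Section 8 remain open. In up to 16 treated subjects, one subject is 1/16 = 6.25 percentage points. An adverse-event rate per subject would shift by that much only if the missed pain event were that subject's sole adverse event.

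This is a cheap improvement that should be made. It is not a flaw that threatens the study.

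**What to change.** In Section 4.3.4.7, record the rating separately for the right and left treatment areas at the time points already scheduled. Apply the existing categories and the existing adverse-event trigger to the higher of the two sides. For secondary outcome 8, report the higher-side score alongside the regional average. State in the instruction to the subject whether the average is over area or over time.

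The cost is one extra field at each of the eight existing time points (before treatment, after treatment and six follow-up visits), with matching CRF and database changes. The wording change needs a protocol amendment under Section 15.2. No extra visit is needed. Pain adverse-event counts may come out slightly higher.

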2.2 POTENTIAL RISKS AND BENEFITS

2.2.1 POTENTIAL RISKS

This treatment modality was designed to inherently minimize the risk to the subject. However, treatment with energy-based modalities (laser, radiofrequency, and plasma devices) produce subsequent heating of the soft tissue that could involve the following commonly Expected Treatment Effects (ETEs): discomfort/pain, edema, erythema, ecchymosis, hypoesthesia, temporary sensory nerve injury (touch sensitivity, itching, temporary numbness/tingling), transient migratory firmness, and temporary and/or transient crepitus.

In addition to commonly expected treatment effects, treatment with the Renuvion APR device could involve the following risks: helium embolism into the surgical site due to inadvertent introduction into the venous or arterial blood supply system, unintended burns (deep or superficial), pneumothorax, temporary or permanent motor nerve injury, ischemia, fibrosis, infection, gas buildup, bleeding, hematoma, seroma, subcutaneous induration, pigmentation changes, increased healing time, unsatisfactory scarring, asymmetry and/or unacceptable cosmetic result.

Subjects using drugs that reduce coagulation (aspirin or NSAIDs) may experience increased bruising or bleeding at the treatment site. Any other medications prescribed for the procedure or after-procedure by the investigator have their own risks; these risks should be discussed with the subject.

A grounding pad is used to ground/neutralize the electrical current. Subjects undergoing radiofrequency treatment will be kept away from contact with metal parts which are grounded, or which have appreciable capacitance to earth.

Risks associated with tumescent anesthesia (lidocaine and epinephrine) include blurred vision, mental/mood changes, drowsiness, dizziness, unusually slow heartbeat, rash, itching, swelling, anxiety, apprehensiveness, restlessness, tremor, weakness, sweating, palpitations, pallor, nausea and vomiting, headache, and respiratory difficulties.

Any unexpected or unforeseen complications will be managed by the investigator throughout the conduct of the study. Unforeseen or unexpected side effects not listed above will be reported to the sponsor and regulatory representatives as they occur.

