4.3.4.8 ADVERSE EVENT REPORTING

The definitions of Adverse Events (AEs) and the subtypes are provided in **Section 8** of the study protocol. Adverse events will be classified by the investigator as to:

Apyx Medical Corporation

Protocol Number: APX-22-04-GR

Effective Date: October 2, 2023

Revision No: 04

Title: A Post-Market Study in Greece of a Minimally Invasive Lower Eyelid Treatment Utilizing the Renuvion System Clinical Trial Protocol

- Anticipated vs unanticipated
- Serious vs not serious
- Expected Treatment Effect (ETE) vs Adverse Event (AE)
- Severity: mild, moderate, severe
- Device and/or procedure causality: not related, related, undetermined

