8. ASSESSMENT OF SAFETY

8.1 SPECIFICATIONS OF SAFETY PARAMETERS

8.1.1 DEFINITION OF AN EXPECTED TREATMENT EFFECT (ETE) AND AN ADVERSE EVENT (AE)

An expected treatment effect is defined as any typical treatment side-effect of the Renuvion APR System of mild to moderate severity and lasting up to a typical maximum duration. An adverse event is defined as any new medical problem, or exacerbation of an existing problem, experienced by a subject while enrolled in the study, whether or not it is considered device-related by the investigator.

An **adverse event** (AE) is any untoward or unfavorable medical occurrence in a human subject, including any abnormal sign (for example, abnormal physical exam or laboratory finding), symptom, or disease temporally associated with the subject's participation in the research, whether or not considered related to the subject's participation in the research.

Apyx Medical Corporation

Protocol Number: APX-22-04-GR

Effective Date: October 2, 2023

Revision No: 04

Title: A Post-Market Study in Greece of a Minimally Invasive Lower Eyelid Treatment Utilizing the Renuvion System Clinical Trial Protocol

A preexisting condition (one that is present at the start of the study) will be recorded as an AE only if the frequency, intensity, or the character of the condition worsens during the study period. Neither the condition, hospitalization, prolonged hospitalization, nor surgery are reported as an AE in the following circumstances: hospitalization or prolonged hospitalization for diagnostic or elective surgical procedures for a preexisting condition. Surgery should not be reported as an outcome of an AE if the purpose of the surgery was elective or diagnostic and the outcome was uneventful.

All ETEs and AEs will be collected during the conduct of this trial.

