8.2 CLASSIFICATION OF AN EVENT

8.2.1 SEVERITY OF EVENT

Each adverse event should be assessed for its severity, or the intensity of an event experienced by the subject, using the following classifications:

- **Mild:** easily tolerated by the subject, causing minimal discomfort, and not interfering with everyday activities. These events generally do not require treatment.
- **Moderate:** sufficiently discomforting to interfere with normal everyday activities. These events are usually relieved by simple therapeutic measures.
- **Severe:** prevents normal, everyday activities. These events may require systemic drug therapy or other medical treatment.

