8.3 TIME PERIOD AND FREQUENCY FOR EVENT ASSESSMENT AND FOLLOW-UP

The occurrence of an AE or SAE may come to the attention of study personnel during a study visit or upon review by a study monitor. All ETEs and AEs will be captured on the appropriate CRF. Information to be collected includes event description, date of onset, clinician's assessment of seriousness and severity, relationship to study device/treatment (assessed only by those with the training and authority to make a determination), actions taken, and date of event resolution. All AEs occurring while on study must be documented appropriately regardless of relationship. All ETEs/AEs assessed as "not yet resolved" must continue to be followed via telephone contact, email or clinic visit every 7 days or sooner as per the physician's direction until event resolution or stabilization.

A pre-existing condition should not be reported as an adverse event unless there has been a substantial increase in severity or frequency of the problem that has not been attributed to natural history. Changes in the severity of an event will be documented to allow for a determination if the event should be re-categorized from an ETE to AE.

Safety evaluations for this study include an interview with the study subject at each follow-up visit by the Investigator or delegated study staff to elicit information about any medical occurrence that meets the definition of Adverse Event. This information will be documented in CRF without regard for cause or relation to device and/or procedure.

Apyx Medical Corporation

Protocol Number: APX-22-04-GR

Effective Date: October 2, 2023

Revision No: 04

Title: A Post-Market Study in Greece of a Minimally Invasive Lower Eyelid Treatment Utilizing the Renuvion System Clinical Trial Protocol

In addition, study subjects will be instructed in the Informed Consent Form, post-procedure take-home instructions, and verbally by study staff to report all complications experienced post study procedure to the site personnel as soon as they occur/are observed. Study staff will ensure that monitoring and management of all adverse events is prioritized. Subjects may be asked to come into the site at any time to assess adverse events.

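### Does it matter that moderate pain is an adverse event in section 4.3.4.7 but could be an expected treatment effect under section 8.1.1?

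*Combined protocol and SAP*

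**What the plan says.** Section 4.3.4.7 divides NRS pain into none (0), mild (1-5), moderate (6-7) and severe (8-10), then states: "Moderate and severe pain/discomfort are considered Adverse Events (AE"). It attaches no duration condition.

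Section 2.2.1 opens its list of "commonly Expected Treatment Effects (ETEs): discomfort/pain, edema, erythema" with pain and sets no score limit. Section 8.1.1 defines an ETE as a typical side effect "of mild to moderate severity and lasting up to a typical maximum duration". No figure is given for that duration.

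The safety endpoint in section 4.3.2 reads: "The primary safety endpoint is an analysis of adverse events through the D180 post-treatment visit". ETEs are not mentioned. Section 10.1 provides for descriptive statistics only and has no rule for tabulating ETEs or AEs. Section 8.1.1 does settle collection: "All ETEs and AEs will be collected during the conduct of this trial".

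**The concern.** A subject with an NRS score of 6 or 7, of ordinary duration and graded mild or moderate by the investigator, meets the AE rule in section 4.3.4.7 and also fits the ETE definition in section 8.1.1. No sentence says which section takes precedence.

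The relation between the two classes is also loose. Section 4.3.4.8 lists "Expected Treatment Effect (ETE) vs Adverse Event (AE") as one of the ways adverse events are classified, which suggests that ETEs are a kind of AE. Section 8.3 provides "to allow for a determination if the event should be re-categorized from an ETE to AE", which suggests two separate classes.

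At stake is the AE count for the primary safety endpoint: two analysts with the same data could report different numbers. With at most 16 treated subjects, a few reclassified events would visibly change a percentage.

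**Working it through.** The plan states no AE rate, safety threshold or precision target, so there is no figure to reproduce. The check is a comparison of the passages, followed by the arithmetic of scale.

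**1. Which pain falls under both rules**

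| Pain event | Section 4.3.4.7 | Section 8.1.1 with 2.2.1 | Overlap |
|---|---|---|---|
| NRS 1-5, graded mild or moderate | not made an AE | may be an ETE | no |
| NRS 6-7, graded mild or moderate, ordinary duration | AE | may be an ETE | yes |
| NRS 8-10, graded mild or moderate, ordinary duration | AE | may be an ETE | yes |
| NRS 6 or more, graded severe | AE | not an ETE | no |

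The overlap is a definite but bounded set of events.

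**2. Whether the text points to one reading**

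Section 4.3.4.7 is specific to pain and unconditional. Section 8.1.1 is a general definition covering every side effect, and section 2.2.1 names pain without a severity. Read together, the specific sentence divides pain at NRS 6 and the general definition covers the rest.

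Section 4.3.4.7 goes on to leave classification of events to the investigator under Section 8, using clinical evaluation, effect on activities and need for mitigation. That sentence is not limited to severe pain. Its criteria resemble the severity grades of section 8.2.1, where moderate means "sufficiently discomforting to interfere with normal everyday activities". The natural reading is that Section 8 supplies the severity grade, while section 4.3.4.7 has already settled AE status. No cross-reference confirms this.

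**3. Whether ETEs are AEs**

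The list in section 4.3.4.8 and the broad AE definition in section 8.1.1 point to a subset. Against that, sections 8.1.1 (on collection), 8.3 and 8.4.1 name ETEs and AEs side by side. Most of the usage treats them as separate classes, so the endpoint in section 4.3.2 most likely means AEs alone. Some ambiguity remains.

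**4. Scale**

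Input: n = 16 treated subjects (sections 4.1 and 10.2, as a maximum). Let k be the number of subjects whose only event is pain in the overlap. The documents give no value for k, so the values below are assumptions.

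Difference in the share of subjects with at least one AE = k/16 if ETEs are left out, and 0 if they are counted:

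- k = 1: 1/16 = 6.25 points
- k = 2: 2/16 = 12.5 points
- k = 4: 4/16 = 25.0 points

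A non-zero difference needs three things together: the table omits ETEs, the investigator records the pain as an ETE despite section 4.3.4.7, and the subject has no other AE. It also takes the share of subjects with an AE as the statistic, which section 4.3.2 does not name.

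For comparison, exact (Clopper-Pearson) 95% intervals at n = 16 are 0 to 20.6% for 0/16, 1.6 to 38.3% for 2/16 and 7.3 to 52.4% for 4/16. Any AE percentage from this study will be imprecise under either reading.

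**5. Whether information is lost**

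ETEs and AEs both go on case report forms, and unresolved events of either class are followed on the same schedule (section 8.3). NRS is recorded before and after treatment and at every follow-up visit (section 4.3.4.7 and Table 6), and it is an outcome in its own right (section 4.3.3). The number of subjects scoring 6 or more at any recorded time can therefore be counted however the event was labelled. Pain that peaks between visits would appear only in the event records, but those hold both classes.

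**The case for a change.** The strongest counter-argument is that a primary safety endpoint should yield one count from one dataset. Here the choice could be made after the data are seen, and section 10.1 schedules a review of all data through Day 90. The ETE duration limit has no number, so the boundary between ETE and AE cannot be applied reproducibly. Section 4.3.4.7 also counts a pain AE as resolved only at a score of zero, with no matching rule for pain recorded as an ETE, so reported durations might differ too. The remedy would cost only wording.

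Part of this stands: there is no cross-reference, the duration limit is undefined for ETEs in general, and section 4.3.2 is silent on ETEs. But the duration limit does not affect the pain rule, which carries no duration condition. A late choice of reading could not reverse a decision, because none depends on the count. The halting rule in section 8.5 rests on judgement and sets no numerical limit.

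Nor is a single pooled ETE-plus-AE table clearly better. The plan calls these effects common, so a pooled subject-level rate could approach 100% and say little. Whether to pool the classes or show them apart is a reporting preference.

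**Conclusion.** No change to the plan is needed. The overlap between sections 4.3.4.7 and 8.1.1 is a gap in detail that analysts fill sensibly: apply the pain-specific sentence as written, and report AEs and ETEs with their labels, alongside the NRS results.

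The possible effect is k/16, or 6.25 points per affected subject, with k unknown, and it arises only if ETEs are omitted from the table. No sample size, test, threshold or decision depends on it.

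This conclusion assumes that all ETEs, AEs and NRS scores are collected as sections 8.1.1 and 4.3.4.7 require, that both classes appear in the report, and that the safety analysis stays descriptive. If the AE rate were later compared with a limit or a reference rate, the count would need a definition first. A cross-reference between the two sections would be tidy, but the study's conclusion would be the same without it. Nothing here decides which classification of pain is clinically right.
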